8.3.2. Missing Date on concomitant medications

In the determination of whether a medication is taken during the Treatment Period, the following rules for missing and partial dates will be applied:

• If the end date is before the first dose of study medication, then the medication is a prior medication, regardless of whether or not the start date is missing or partially missing

Life Sciences

- If the end date is on or after the date of the first dose of study medication, then the following rules will be applied for missing or partially missing start dates:
 - If the start date is completely missing, then the medication will be assumed to be concomitant.
 - If only the year of the start date is recorded and the year is either before or the same year as the date of last dose of study medication then the medication will be assumed to be concomitant.
 - If only the year of the start date is recorded and the year is after the year of the date of last dose of study medication, it will be considered as a post-study treatment medication.
 - If only the year and the month of the start date is recorded and the month specified is either before or the same month as the date of last dose of study medication, then the medication will be assumed to be concomitant.
 - If only the year and the month of the start date is recorded and the month specified is after the month of the date of last dose of study medication, it will be considered as a post-study treatment medication.

The same rules are applicable for the concomitant procedures.

8.3.3. Questionnaires Missing Data

See Section 4.3 for the questionnaires and Appendix 12.3 for Scoring guidelines.

In cases where individual items are skipped, subscale scores can be prorated using the average of the other answers in the scale. A FACIT measure is considered to be an acceptable indicator of patient quality of life as long as overall response rate at item level is greater than 80% (e.g., at least 22 of 27 FACT-G items completed). This is not to be confused with individual subscale item response rate, which allows a subscale score to be prorated for missing items if greater than 50% of items are answered e.g., a minimum of 4 of 7 items, 4 of 6 items, etc. The total score is then calculated as the sum of the un-weighted subscale scores. In addition, a total score should be calculated only if ALL of the component subscales have valid scores.

PGIC and PGIS questionnaires have no score derivation.

8.3.4. Overlapping/Duplicated Diaries

In some patients questionnaires recorded at screening visit (expected to be done between Day -7 and Day -1) were actually filled in on Day 1, just before the questionnaire filled in for the Visit 2, meaning that the date of screening assessment is the same as the date of Visit 2. These cases were checked during BDRM and minor protocol deviations were recorded.

In some patients the overlapping of assessment dates happened between Visit 3 and Visit 10. The same questionnaire was performed twice (with a lag of few minutes) in a day (usually corresponding to the Day of a given Visit X). The second questionnaire

was entered as performed at the Visit X, while the first one was entered as referring to the prior Visit (X-1). For these cases the following rule will be applied:

If the date of assessment [Visit (X-1)] >= date of assessment Visit (X),

then the date and collected value of questionnaire assigned to Visit X-1 will be set to missing. The date of assessment Visit (X-1) will be subsequently reset to the date of Visit (X-1) from Study Visits domain; this will be done at ADaM level. Questionnaire value set to missing will be imputed according to the rules described in Appendix 12.1.

If a mismatch between the date of score assessment (i.e.: questionnaire date aforementioned) and the date of corresponding individual items assessment is detected, the date of score will be replaced with the date of individual items. If a mismatch between the dates of individual items assessment is detected, the maximal date will be used to replace the date of score.

8.3.5. Missing Date on Adverse Events

In the determination of whether an Adverse Event is Treatment Emergent (TEAE), the following rules for missing and partial dates will be applied:

- If an incomplete onset date was collected for an AE, the event will be considered TEAE unless there is other evidence that confirms that the event was not TEAE (e.g.; next bullet point)
- If the AE end date is before the first dose of study medication, then the AE is pre-treatment, regardless of whether or not the AE start date is missing or partially missing.

8.4. Covariates

Business & Decision

Life Sciences

The three stratification factors at randomization are used as categorical covariates in each statistical model:

- Systemic anti-cancer treatment line (first line vs second line vs third or higher line)
- Cancer treatment (immunotherapy vs no immunotherapy)
- The 5-item Anorexia Symptom Subscale (≤10 vs >10).

8.5. Interim Analysis

Not applicable. No formal interim analysis is planned for this study.

8.6. Subgroups analyses

Subgroup analyses (specifically the analysis of the coprimary and secondary efficacy endpoints) will be performed for the subgroups for which numerical feasibility was confirmed at the BDRM, as defined by the following variables:

HELSINN

T AN001 Effective Date 25 JUL 2022 Approved Version 2.00

- Age (≤ 65 years or > 65 years)
- Gender
- Systemic anti-cancer treatment line (first line vs second line vs third or higher line) – stratification factor
- Cancer treatment (immunotherapy vs no immunotherapy) stratification factor
- The 5-item Anorexia Symptom Subscale (≤10 vs >10) stratification factor
- Patients who completed 24 weeks treatment

8.7. Visit windows

For the endpoints based on mean change and duration of benefit, the actual day of assessment will be used for the computation. No other visit windowing is applicable and planned to be done apart from corrections related to the overlapping/duplicated diaries described in Section 8.3.4.

8.8. Definitions

Baseline

The baseline value for all efficacy analyses is defined as the value collected at Visit 2 (randomization); if this is not available or collected day(s) later as compared to Visit 2, the value collected at screening visit will be used.

For the following assessments, baseline is the value reported at Screening (V1):

- ECOG PS
- HbA1c
- all Urinalysis parameters
- the Patients' Global Impression of Severity (PGIS) scale
- the Patients' Global Impression of Change (PGIC) scale

The baseline value for all safety analyses is defined as the last measurement performed before study drug administration.

Change from Baseline

Any "Change from baseline" variable will be computed as: "variable" at Visit X – Baseline, with X \geq 3 and Baseline defined as above.

Last assessment

Last assessment performed (body weight / 5-IASS) regardless of treatment discontinuation.

Retrieved dropout

Patient who drops the treatment but who continues to be assessed.

Non-monotone pattern of missingness (also called "Intermittent missing values")

Missing values may occur in the middle of a subject record (e.g., missed intermediate visit). It is expected that a value before the missing assessment, and a value after the missing assessment are available.

Monotone pattern of missingness (also called "non-Intermittent missing values")

Missing values are located in a block at the end of data records (e.g., due to study discontinuation).

Study Treatment Start Date

It is the date of the first intake of the study treatment.

End of Treatment (EOT) Date

It is the date declared in the End of Treatment CRF Form. This date will be used in the derivations unless specific adjustments are needed (e.g., for actual exposure derivation).

Last follow-up contact date

It is the date of the last contact for patients alive. It is the date of last follow-up in case of final phone contact (Visit 11 for patients completing the study, before Visit 11 in case of treatment discontinuation), or the date of last performed visit in case of patient lost to follow-up.

It corresponds to the date of death in case a patient died.

Study completion

A patient will be defined as having "completed" the study when the patient completes Visit 11. Termination of the study before performing Visit 11 will be considered as a premature study discontinuation.

Patients who completed 24 weeks treatment

A patient will be defined as having "completed" 24 weeks treatment when the patient received study drug at the day of Visit 10 (either on-site or at home) and have evidence of treatment for all previous weeks.

Fluid retention

Presence of fluid retention will be assumed when either a treatment emergent AE associated with fluid retention is present or edema is recorded in the CRF by investigator at time of the assessment of weight. Specific assessments are scheduled at each study visit.

After a specific review of the LLTs during the BDRM, AEs coded with the following PTs were confirmed as possibly impacting the weight measurements: 'Fluid retention', 'Ascites', 'Pleural effusion', 'Oedema peripheral', 'Oedema'. These AEs will be taken into account.

Clinically meaningful thresholds for 5-IASS change and Body Weight Change

To support with patient informed interpretation of meaningful change or stabilization, the results of a quantitative analysis of a separate study (7), combined with evidence from the embedded qualitative interview sub-study (6), support a responder definition of 3.0 for the 5-IASS Score and 1.5 kg weight gain for body weight.

These thresholds were defined in line with FDA guidance, therefore anchor-based methods for score interpretation were considered the primary analysis. Distribution-based methods were used as supportive and secondary analysis using PGIS (Patient Global Impression of Severity) and PGIC (Patient Global Impression of Change) as anchors.

For the analysis of the duration of treatment benefit the definition of a threshold to establish a change from baseline as clinically meaningful is provided (Sections 10.2 and 10.2.1)

Last value

Business & Decision

Life Sciences

For Laboratory Shift Tables analysis, the Last Value is the last value reported by the patient during the study period.

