If patient is confirmed eligible, authorized study personnel will proceed with randomization procedures. The IWRS will provide the study kit number to be dispensed to the patient **only after** all the following pre-dose assessments are completed for baseline measurements:

- Laboratory assessments, including:
 - Chemistry,
 - Hematology.
- Body weight via scale measurement, to be done prior to study drug administration.
- 12-Lead ECG pre dose, in triplicate.
- A dedicated physical examination with focus to monitoring signs and symptoms of edema (see Section 7.2.2.1 for details); results of this PE will be inserted in source data and in the relevant pages of eCRF.
- Vital signs (including pulse rate, systolic and diastolic blood pressure after at least 5 minutes rest in semi-supine position, respiratory rate and body temperature).
- Adverse events recording.
- Prior and concomitant medications (not including NSCLC treatment) recording.
- Administration and completion of:
 - FACIT questionnaires (includes all 4 domains PWB, FWB, SWB, and EWB of FACT-G, 12-item A/CS domain and 13-item FACIT-F fatigue domain),
 - Hunger Assessment Scale questionnaire.
- Once completed these pre-dose assessments the patient will be "randomized" and new study kit will be dispensed.
- CT scan for tumor assessment. The baseline tumor assessment may have been obtained within 28 days prior the first dose of study drug (see Section 7.2.7).
- Study drug will therefore be administered. The date and the precise time (hh:mm) of the study drug must be recorded in the source records as well as on the relevant eCRF page.
- One hour post study drug administration patient will undergo ECG measurement in triplicate.

- NSCLC treatment regimen will be collected at Baseline and any dose adjustments, as and if applicable.
- Before leaving the clinic, the patient will be reminded about the prohibited concomitant medications (see Section 5.13.2 for details).
- Patient will also be reminded to come back to clinical site in 3 weeks for next visit and be reminded to arrive at the hospital under fasting conditions.

6.1.3 Visit 3 (Day 22+3): Week 3

The patient will return to the trial site on Visit 3, at Day 22 (+3), approximately 3 weeks after Visit 2. Patient will arrive at the hospital under fasting conditions.

The patient will undergo the following procedures/assessments:

- Study drug administration.
- Laboratory assessments, including:
 - o Chemistry,
 - Hematology.

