7.2.4 Height and BMI

Height will be measured in cm at the Screening Visit (Day -7 to -1, Week -1), and BMI will also be calculated and recorded.

7.2.5 12-lead ECG

12-lead ECGs will be conducted in triplicate at each visit Screening Visit, Visit 2 (Week 1), Visit 3 (Week 3), Visit 4 (Week 6), Visit 5 (Week 9), Visit 6 (Week 12), Visit 7 (Week 15), Visit 8 (Week 18), Visit 9 (Week 21), and Visit 10 (Week 24). These 12-lead ECGs will be obtained in triplicate at each time-point and the reading will be carried out at a central facility by an independent cardiologist blind to the study treatment. Any new or worsening ECG abnormalities assessed to be clinically significant by each study investigator will be reported as adverse events.

ECG will be recorded in triplicate at 1 hour (± 5 minutes) post dose at each visit to align with occurrence of C_{max} , with the exception of Screening Visit (where ECG will be taken only pre-dose) and Visit 2, Day 1, where ECG will be taken also at pre-dose.

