11.5. Electrocardiogram (ECG)

Life Sciences

Business & Decision

Shift tables from baseline to the worst post-baseline results will be provided for the ECG overall interpretation. The following categories will be used: normal, abnormal and not clinically significant, abnormal and clinically significant. The frequencies of ECG overall interpretation by visit as well as the number and percentage of patients who performed the assessment will be also tabulated.

ECG measurements (HR, QT, QTcF, QTcB, PR, RR, and QRS) will be summarized using descriptive statistics by treatment group and visit. The change from baseline will also be summarized in the same manner.12-lead ECGs measurements are obtained in triplicate. Analysis will be performed using the average of the three measurements. In case of one or two measurements are missing the average will be calculated on the bases of the available measurements. Summaries showing the number and percent of patients with outlier values will be presented by treatment.

ECG interval	Categorical outlier criteria
QTcF	Treatment-emergent value of > 450 and ≤ 480 ms when not present at baseline (new onset)
	Treatment-emergent value of > 480 and ≤ 500 ms when not present at baseline (new onset)
	Treatment-emergent value of > 500 ms when not present at baseline (new onset)
	Increase of QTcF from baseline of > 30 and \leq 60 ms
	Increase of QTcF from baseline > 60 ms
PR	Increase of PR from baseline > 25% resulting in PR > 200 ms
QRS	Increase of QRS from baseline > 25% resulting in QRS > 120 ms
HR	Decrease of HR from baseline >25% resulting in HR < 50 bpm
	Increase of HR from baseline >25% resulting in HR > 100 bpm

Outlier values will be identified using the following criteria:

Any treatment emergent clinically significant ECG abnormality will be reported as an AE.

All ECG data will be listed by patient.

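### The SAP's change-from-baseline rule starts at Visit 3, so read literally it leaves the first-dose ECG at Visit 2 out of the ECG change summaries and, by inference, out of six outlier criteria

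*SAP*

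**What the plan says.** SAP 8.8 (Definitions) gives one general rule for change from baseline. It is worded to cover any such variable and takes the value at Visit X minus baseline, "with X \geq 3 and Baseline defined as above". The baseline definitions just above it include the safety one: "The baseline value for all safety analyses is defined as the last measurement performed before study drug administration".

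Protocol 6.1.2 (Visit 2, Day 1) lists a pre-dose triplicate ECG, then the first dose, then a further recording: "One hour post study drug administration patient will undergo ECG measurement in triplicate". Protocol 7.2.5 (12-lead ECG) repeats the schedule. ECGs are taken one hour after dosing at each visit to coincide with Cmax. The exceptions are Screening, which is pre-dose only, "and Visit 2, Day 1, where ECG will be taken also at pre-dose".

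SAP 11.5 (Electrocardiogram) summarises HR, QT, QTcF, QTcB, PR, RR and QRS by treatment group and visit, and adds: "The change from baseline will also be summarized in the same manner". It then lists categorical outlier criteria, several of them worded as a movement from baseline, for example "Increase of PR from baseline > 25% resulting in PR > 200 ms". It gives no ECG-specific definition of change, names no visits for the outlier table and does not mention the Visit 2 post-dose recording.

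**The concern.** For body weight and the questionnaires, Visit 2 is the baseline visit, so starting change values at Visit 3 loses nothing. ECG differs because Visit 2 holds a reading on each side of the first dose. The pre-dose triplicate is the baseline under the safety definition, and the one-hour triplicate is a true on-treatment value. A rule keyed to visit number cannot tell them apart and discards the second.

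That reading is the trial's only ECG after a first dose. It is also the tightest within-patient contrast available, since both recordings fall at one visit whereas Visit 3 comes about three weeks later. The intervals matter to this programme: protocol 1.2.2 reports transient PR, QRS and QT prolongation at 300 and 400 mg, and drugs that may prolong PR or QRS are excluded in 4.3.3 and prohibited in 5.13.2. PR and QRS have no outlier criterion based on an absolute value alone, so if the change value is not computed, a first-dose PR or QRS outlier cannot be counted.

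**Working it through.** The SAP states no figure to reproduce here. The check is a reading of the text plus two counts.

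**Is the Visit 2 post-dose ECG post-baseline?** The safety baseline is the last measurement before study drug. Protocol 6.1.2 places one triplicate before the first dose and one an hour after it. The second is therefore post-baseline.

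**Does the rule admit it?** The rule needs X of at least 3, and this recording belongs to Visit 2. Reading X as a week number makes no difference, because Visit 3 is Week 3 and Visit 2 is labelled Week 1. It is not admitted.

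**Does another definition override the rule?** SAP 10.3.1.5 defines change for the exploratory efficacy endpoints at Weeks 3 to 24. SAP 11.5 gives no definition. That leaves 8.8 as the only general one.

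**Scheduled post-dose ECG time points (protocol 7.2.5):**

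| Period | Visits | Scheduled | With X ≥ 3 | Left out |
|---|---|---|---|---|
| Whole treatment period | 2 to 10 | 9 | 8 | 1/9 = 11% |
| Up to Week 12 | 2 to 6 | 5 | 4 | 1/5 = 20% |

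**Outlier criteria in SAP 11.5:**

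| Interval | Absolute new-onset value only | Needs a change from baseline |
|---|---|---|
| QTcF | 3 (bands above 450, 480 and 500 ms) | 2 (rise >30 to ≤60 ms; rise >60 ms) |
| PR | 0 | 1 (rise >25% to above 200 ms) |
| QRS | 0 | 1 (rise >25% to above 120 ms) |
| HR | 0 | 2 (fall >25% to below 50 bpm; rise >25% to above 100 bpm) |
| Total | 3 | 6 of 9 |

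**Which ECG outputs does the rule reach?** The by-visit change summaries are reached directly, through 8.8. The six change-based criteria are reached by one step of inference: 11.5 does not say which visits count, and 8.8 is the only definition of change available to fill that gap. Five outputs are not built on a change variable and so are not reached: the absolute values by visit, the interpretation frequencies by visit, the shift table to the worst post-baseline interpretation, the three absolute QTcF criteria and the listings.

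**When does a patient lose every ECG change value?** Any ECG from Visit 3 to Visit 10 yields one, so total loss needs no ECG at Visit 3 or at any later visit.

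**A related gap.** SAP 11.5 averages the three measurements of a triplicate and reports by visit. Visit 2 has two triplicates, six recordings in all, and the text does not say that they are averaged separately.

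**The case against.** The strongest reply is that the Visit 3 start was probably written with efficacy in mind and will not be applied to ECG. SAP 11.5 summarises the measurements by visit and handles change in the same way; Visit 2 is an ECG visit, so the section can be read as including it. The outlier table speaks only of movement from baseline, which can be judged on any post-baseline recording. The mock tables that would settle this are a separate document (SAP 12.5), not available here. This stands as doubt about what will be programmed. It does not remove the defect: if the intended output includes the Visit 2 post-dose value, the rule in 8.8 contradicts it and needs correcting anyway.

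The safety background is also milder than a partial reading suggests. Protocol 1.2.2 places the prolongations at 300 and 400 mg, against 100 mg here. It reports no QTcF above 450 ms, says the investigator judged the increases not clinically significant, and cites a thorough QT study with no meaningful effect on ventricular repolarization. That conclusion concerns repolarization and does not itself settle PR or QRS. The one-hour post-dose ECG is also repeated at eight later visits, so what is at risk is the first-dose reading and not every reading near Cmax.

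Two stronger readings are tempting, and the documents support neither.

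- A reader might infer that the Visit 2 reading disappears from the ECG report. It does not; the five outputs named in the check keep it, and any clinically significant abnormality is still reported as an adverse event.
- A reader might infer that a patient who misses the Visit 3 ECG contributes no change value at all. A later ECG is enough. Protocol 6.3 asks patients who stop study drug to keep attending to Week 24, and the flow chart asks early withdrawals for the Week 9 procedures, which include an ECG.

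**Conclusion.** The point holds in a limited form. Under the stated rule, an ECG that the protocol requires, and that is post-baseline by the SAP's own definition, has no place in the change-from-baseline summaries. Its absence from the six change-based outlier criteria is a reasonable inference, not something the SAP states.

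The size is 1 of 9 scheduled post-dose time points (1 of 5 up to Week 12), and it is the only first-dose one. These are counts of scheduled time points, not of patients. The documents do not say how many patients have no ECG after Visit 2, so the number losing every change value is unknown. Patients who start on Day 2 because they were not fasting (protocol 5.8) may have no Visit 2 post-dose ECG to lose.

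SAP 13 does not list this among the safety changes from the protocol, which fits an oversight better than a decision. ECG analysis here is descriptive; no test and no efficacy conclusion depends on it. The correction is worth making because it repairs a stated rule at almost no cost.

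**What to change.** In SAP 8.8, reword the rule to: *Visit X − Baseline, with X ≥ 3; for ECG also the Visit 2 one-hour post-dose recording*.

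In SAP 11.5:

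- show Visit 2 pre-dose (the baseline) and Visit 2 post-dose as separate time points, and average each triplicate separately;
- include the Visit 2 post-dose value in the change table;
- include it in all six change-based outlier criteria.

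The cost is one added clause in 8.8, a short clarification in 11.5 and one labelled time point in the ECG tables, with matching edits to the mock tables if they do not already have it. No new data are needed, and alpha, the efficacy analyses and the other safety outputs are untouched.

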7.2.2.1 Monitoring Signs and symptoms of edema

Since excess in body water may contribute to a change in body weight and confound the primary efficacy analysis, all patients will be monitored for the signs and symptoms of edema during the study. Signs and symptoms of edema will be recorded in patient charts at each study visit. For scheduling details see study flow chart.

A dedicated PE aiming to monitor signs and symptoms of edema should be performed on limbs, abdominal and thoracic landmarks. Edema should be evaluated for pitting, tenderness to palpation (by applying pressure), and skin temperature, color, and texture changes.

Limbs Edema:

PE should focus on dorsum of the foot, all foot including ankle, the medial malleolus, and the bony portion of the tibia. In general, PE should focus on the assessment of edema involving all part of limb distal to middle point (knee, elbow), all limb involved from proximal joint (hip, elbow), and all limbs.

Abdominal and Thoracic Edema

PE should focus on visual and palpation assessment of the abdominal area, while for the evaluation of thoracic edema will be complemented by auscultation.

Data of patients with fluid retention will be handled as described in Section 9.4.1.

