8.9. Other Considerations: Handling impact of COVID-19 pandemic

The present document and the analysis described in it, have been updated in compliance with the FDA **guidance** contained in the Conduct of Clinical Trials of Medical Products during the Covid-19 Public Health Emergency (Version March 2020, updated on August 30th 2021).

The Sponsor provided instructions to sites during the study in order to manage and mitigate the COVID-19 pandemic effects on the study, particularly allowing remote subject visits (refer to the Guidance and contingency plan from Sponsor to Sites (8)).

8.9.1. Handling Impact of COVID-19 in the Statistical Analysis All deviations related to the COVID-19 pandemic and resulting from the measures described in the Sponsor's contingency plan have been captured and discussed during the BDRM.

Sensitivity analyses have been planned based on the following considerations. Upfront it can be stated that:

- A tangible impact on measurements of body weight can be expected. Body weight values were reported by patient at each visit during a phone call. Patients were asked to use their own weight scale (analog or digital). This implies a lack of standardization and therefore to a certain degree of variability and lower accuracy.
- A minor impact is anticipated on eCOA endpoints. During remote visit on the phone, patient was asked to respond to each item of each questionnaire as per schedule at the given visit by delegated study personnel who entered responses in eCOA system accordingly, and data underwent to standard transmission process.
- There is no reason to expect any worsening in patient safety.

T AN001 Effective Date 25 JUL 2022 Approved Version 2.00

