10.1.3.2. Fluid retention replacement analysis

As fluid retention may possibly influence the weight increase, a sensitivity analysis will be performed for the primary endpoint "Mean change in body weight from baseline over 12 weeks", by considering as missing the values obtained in presence of fluid retention (for the definition of fluid retention, see Section 8.8 "Definitions").

Those missing values will be therefore imputed on the basis of the following rules for imputation:

- In case of one or more body weight assessments measured in presence of fluid retention, comprised between two assessments (pre- and post-) measured in absence of fluid retention, the lower value between the assessed weight(s) and the weight(s) estimated by the linear interpolation between pre- and postassessments will be imputed.
- If no subsequent values observed in absence of fluid retention are available, the post-baseline weight(s) recorded in presence of fluid retention will be imputed with the baseline value if that value is lower than the recorded value. Otherwise the recorded value will be used
- If fluid retention is already present at baseline (due to protocol violation), no imputation will be performed and observed values will be analyzed.

After imputation of these values, the imputation rule for the non-intermittent missing values described in Appendix 12.1 will be applied.

Furthermore, an additional sensitivity analysis will be performed for the primary endpoint "Mean change in body weight from baseline over 12 weeks", by excluding the patients for which fluid retention was reported at any time during the study.

HELSINN

T AN001 Effective Date 25 JUL 2022 Approved Version 2.00

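### The fluid-retention sensitivity analysis has no 'not assessed' state, so a home weight from a telephone visit counts as fluid-free unless a fluid-related TEAE is present

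*SAP*

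**What the plan says.** **Definition.** SAP 8.8 assumes fluid retention when a fluid-related TEAE is present or when "edema is recorded in the CRF by investigator at time of the assessment of weight". The TEAE trigger covers five preferred terms. The SAP adds: "Specific assessments are scheduled at each study visit". No category exists for a visit at which oedema was not assessed.

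**Examination.** Protocol 7.2.2.1 describes a physical examination: "Edema should be evaluated for pitting, tenderness to palpation (by applying pressure), and skin temperature, color, and texture changes". Auscultation is added for the thorax. The same section gives the reason: excess body water may confound the primary efficacy analysis.

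**Remote visits.** On the telephone visits allowed during the pandemic, SAP 8.9.1 states: "Body weight values were reported by patient at each visit during a phone call". Patients used their own scales. The section discusses weight accuracy, questionnaires and safety, but not the oedema examination.

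**Replacement rule.** SAP 10.1.3.2 works with two states.
- A fluid-affected weight "comprised between two assessments (pre- and post-) measured in absence of fluid retention" is replaced by "the lower value between the assessed weight(s) and the weight(s) estimated by the linear interpolation".
- If no later weight without fluid exists, the baseline weight is used when it is lower than the recorded one.
- A second analysis drops patients with fluid retention reported at any time.

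**Home weights.** SAP 10.1.3.3 sets weights collected at home to missing. This is a separate analysis, and the fluid rule is not applied within it.

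**The concern.** The fluid analyses exist to show that the weight co-primary endpoint is not driven by fluid. They carry more of that burden because SAP 13 drops the planned fluid-retention subgroup for lack of numbers.

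At a telephone visit one of the two triggers is presumably unavailable, and the rule then reads a missing examination as absence of fluid. A home weight that carries fluid, with no fluid-related TEAE present, has three effects:
- it stays in the analysis as recorded;
- it can be the pre- or post-anchor that sets the replacement for a neighbouring on-site weight at which oedema was found;
- because it looks like a later fluid-free value, it can replace the stricter baseline rule with the milder interpolation rule.

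The exclusion analysis has the same blind spot for patients whose fluid appeared only at remote visits and was not reported as an AE. A reassuring result could therefore partly reflect missing ascertainment, and the report as planned would not show how often that happened.

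**Working it through.** The plan states no figure on this point, so there is none to reproduce. The check applies the rule of SAP 10.1.3.2 to constructed patients.

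**Inputs.**
- From the SAP: replacement = min(recorded, interpolated between the nearest fluid-free weights); if no later fluid-free weight exists, min(recorded, baseline). Mean change = sum of changes divided by the number of assessments, taken here as the four visits at Weeks 3, 6, 9 and 12.
- Assumed for illustration: dry weight 50 kg throughout, so the true change is 0, and 2 kg of fluid when present. Home weights carrying fluid have no fluid-related TEAE, except in the 'TEAE present' column.

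**Patterns.**
- A: Week 3 dry on site; Week 6 oedema on site (52); Weeks 9 and 12 at home with fluid (52, 52).
- B: Week 3 oedema on site (52); Week 6 at home with fluid (52); Weeks 9 and 12 dry.
- C: Week 3 dry; Weeks 6 and 9 oedema on site (52, 52); Week 12 at home with fluid (52).
- D: only Week 6 at home with fluid (52); the rest dry.

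**SAP rule as written.**
- A: Week 6 lies midway between 50 and 52, so min(52, 51) = 51. Mean (0 + 1 + 2 + 2)/4 = 1.25 kg.
- B: Week 3 lies midway between baseline 50 and Week 6 at 52, so 51. Mean (1 + 2 + 0 + 0)/4 = 0.75 kg.
- C: Week 6 = 50 + 2 × 3/9 = 50.67; Week 9 = 50 + 2 × 6/9 = 51.33. Mean (0 + 0.67 + 1.33 + 2)/4 = 1.00 kg.
- D: nothing is flagged. Mean (0 + 2 + 0 + 0)/4 = 0.50 kg.

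**Comparison (mean change, kg; truth = 0).**

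| Pattern | No fluid handling | SAP rule as written | TEAE present at home visits | Home weight barred as anchor but kept |
|---|---|---|---|---|
| A | (0+2+2+2)/4 = 1.50 | 1.25 | 0 | (0+0+2+2)/4 = 1.00 |
| B | (2+2+0+0)/4 = 1.00 | 0.75 | 0 | (0+2+0+0)/4 = 0.50 |
| C | (0+2+2+2)/4 = 1.50 | 1.00 | 0 | (0+0+0+2)/4 = 0.50 |
| D | (0+2+0+0)/4 = 0.50 | 0.50 | 0 | 0.50 |

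The rule as written never exceeds the result with no fluid handling, but it can fall well short of full correction. In A and C the unexamined home weight also switches off the baseline rule, which would otherwise return the flagged on-site weights to 50 kg. Barring the anchor removes the carry-over only. The home weight's own fluid leaves the analysis only if that weight is set to missing.

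**Between-arm scale.** The documents give neither the number of home weights nor the oedema rate. Assume home weights are 5 to 20% of visits, the between-arm excess of undetected fluid at those visits is 5 to 10 percentage points, and the fluid weighs 1 to 3 kg.
- Direct effect = home share × excess × kg.
- Low: 0.05 × 0.05 × 1 = 0.0025 kg, which is 0.14% of 1.8 kg.
- High: 0.20 × 0.10 × 3 = 0.06 kg, which is 3.3% of 1.8 kg.

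Some anchor carry-over would be added to this.

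**The case against.** The strongest reply is that the TEAE trigger covers most of the gap. AEs are obtained by asking the patient (Protocol 8), which works by telephone, as at Visit 11. New or worsening examination findings should be entered as AEs (Protocol 7.2.2; SAP 11.6 for clinically significant ones), and unresolved AEs are recorded as ongoing (Protocol 8.1.2). In pattern A the Week 6 oedema should then be an open AE at Weeks 9 and 12. Those weights would be flagged and the existing rule would give 0 kg. This stands: +1.25 kg arises only if no such AE was filed or it was closed early. It does not cover fluid that only an examination would find, nor fluid that first appears at a remote visit and is not volunteered.

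Several further points also stand. The remote-visit instruction (SAP reference 8) is not supplied and may include questions about swelling. COVID-19 deviations were discussed at the blinded data review meeting. The COVID-19 analysis removes all home weights, and the exclusion analysis would remove patients A, B and C, whose oedema was recorded on site. None of this gives the fluid rule a 'not assessed' state or applies both rules in one run.

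A reader might infer that a weight with no oedema recorded is always taken as fluid-free. The definition does not say that, because a fluid-related TEAE also flags the weight. A reader might also infer that the primary weight result is inflated by this gap. The documents do not support that either: the gap lies in sensitivity analyses outside the multiplicity procedure, and the lower-value rule means no recorded weight is raised above its value in the primary analysis.

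**Conclusion.** The point holds in a limited form. For a home weight with no fluid-related TEAE present, the plan treats an examination that was presumably not done as evidence of no fluid, in the analysis meant to address fluid. The error runs one way, towards under-correction.

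The size cannot be determined from the documents and is probably small: about 0.003 to 0.06 kg between arms on the assumptions above, plus some carry-over. The patient-level figures of 0.50 to 1.25 kg illustrate how the rule behaves with an assumed 2 kg of fluid. They should not be set against the 1.8 kg between-arm planning effect as if they were the same kind of quantity. The conclusion rests on the inference that oedema was not examined by telephone. It concerns how far the fluid sensitivity analysis can be relied on, not the primary test.

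**What to change.** By SAP addendum before unblinding:

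1. In SAP 8.8, derive a flag 'fluid status not assessed' for any weight with no oedema examination at that visit and no fluid-related TEAE present.
2. In SAP 10.1.3.2, do not let such a weight serve as a fluid-free pre- or post-anchor, or count as the later fluid-free value that displaces the baseline rule, unless fluid status is otherwise documented.
3. Add one combined run: set home weights to missing as in SAP 10.1.3.3, then apply the fluid-retention rule, then impute what remains missing. This also deals with fluid that first appears at a remote visit, which step 2 alone leaves in (pattern D).
4. Report the number of not-assessed weights by arm, so that a reader can judge the replacement and exclusion analyses.

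The cost is one derived flag and one extra run, with no new data collection. The downside is a few more imputed weights and slightly less precision in a sensitivity analysis.
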